7.4.2 Safety Monitoring Committee (SMC)

This protocol will require oversight from the Safety Monitoring Committee (SMC). Initial review will occur as soon as possible after the annual NIH Intramural IRB continuing review date. Subsequently, each protocol will be reviewed as close to annually as the quarterly meeting schedule permits or more frequently as may be required by the SMC. For initial and subsequent

reviews, protocols will not be reviewed if there is no accrual within the review period. Written outcome letters will be generated in response to the monitoring activities and submitted to the Principal investigator and Clinical Director or Deputy Clinical Director, CCR, NCI.

8 SPONSOR PROTOCOL/SAFETY REPORTING

8.1 DEFINITIONS

8.1.1 Adverse Event

Any untoward medical occurrence in a patient or clinical investigation subject administered a pharmaceutical product and which does not necessarily have a causal relationship with this treatment. An adverse event (AE) can therefore be any unfavorable and unintended sign (including an abnormal laboratory finding), symptom, or disease temporally associated with the use of a medicinal (investigational) product, whether or not related to the medicinal (investigational) product (ICH E6 (R2))

8.1.2 Serious Adverse Event (SAE)

An adverse event or suspected adverse reaction is considered serious if in the view of the investigator or the sponsor, it results in any of the following:

- Death,
- A life-threatening adverse event (see **8.1.3**)
- Inpatient hospitalization or prolongation of existing hospitalization
 - A hospitalization/admission that is pre-planned (i.e., elective or scheduled surgery arranged prior to the start of the study), a planned hospitalization for pre-existing condition, or a procedure required by the protocol, without a serious deterioration in health, is not considered a serious adverse event.
 - A hospitalization/admission that is solely driven by non-medical reasons (e.g., hospitalization for patient convenience) is not considered a serious adverse event.
 - Emergency room visits or stays in observation units that do not result in admission to the hospital would not be considered a serious adverse event. The reason for seeking medical care should be evaluated for meeting one of the other serious criteria.
- Persistent or significant incapacity or substantial disruption of the ability to conduct normal life functions
- A congenital anomaly/birth defect.
- Important medical events that may not result in death, be life-threatening, or require hospitalization may be considered a serious adverse drug experience when, based upon appropriate medical judgment, they may jeopardize the patient or subject and may require medical or surgical intervention to prevent one of the outcomes listed in this definition.

8.1.3 Life-threatening

An adverse event or suspected adverse reaction is considered "life-threatening" if, in the view of either the investigator or sponsor, its occurrence places the patient or subject at immediate risk of death. It does not include an adverse event or suspected adverse reaction that, had it occurred in a more severe form, might have caused death. (21CFR312.32)

8.1.4 Severity

The severity of each Adverse Event will be assessed utilizing the CTCAE version 5.0.

8.1.5 Relationship to Study Product

All AEs will have their relationship to study product assessed using the terms: related or not related.

- Related – There is a reasonable possibility that the study product caused the adverse event. Reasonable possibility means that there is evidence to suggest a causal relationship between the study product and the adverse event.
- Not Related – There is not a reasonable possibility that the administration of the study product caused the event.

8.2 ASSESSMENT OF SAFETY EVENTS

AE information collected will include event description, date of onset, assessment of severity and relationship to study product and alternate etiology (if not related to study product), date of resolution of the event, seriousness and outcome. The assessment of severity and relationship to the study product will be done only by those with the training and authority to make a diagnosis and listed on the Form FDA 1572 as the site principal investigator or sub-investigator. AEs occurring during the collection and reporting period will be documented appropriately regardless of relationship. AEs will be followed through resolution.

SAEs will be:

- Assessed for severity and relationship to study product and alternate etiology (if not related to study product) by a licensed study physician listed on the Form FDA 1572 as the site principal investigator or sub-investigator.
- Recorded on the appropriate SAE report form, the medical record and captured in the clinical database.
- Followed through resolution by a licensed study physician listed on the Form FDA 1572 as the site principal investigator or sub-investigator.

For timeframe of recording adverse events, please refer to section **6.1**. All serious adverse events recorded from the time of first investigational product administration must be reported to the sponsor.

Abbreviated Title: Phase II Study LB100 gliomas

Version Date: 06/02/2022

8.3 REPORTING OF SERIOUS ADVERSE EVENTS

Any AE that meets protocol-defined serious criteria or meets the definition of Adverse Event of Special Interest that require expedited reporting must be submitted immediately (within 24 hours of awareness) to OSRO Safety using the CCR SAE report form.

All SAE reporting must include the elements described in [8.2](#)

SAE reports will be submitted to the Center for Cancer Research (CCR) at:

[contact] and to the CCR PI and study coordinator. CCR SAE report form and instructions can be found at:

<https://ccrod.cancer.gov/confluence/display/CCRCRO/Forms+and+Instructions>

Following the assessment of the SAE by OSRO, other supporting documentation of the event may be requested by the OSRO Safety and should be provided as soon as possible.

8.5 REPORTING PREGNANCY

All required pregnancy reports/follow-up to OSRO will be submitted to:

[contact] and to the CCR PI and study coordinator. Forms and instructions can be found here:

<https://ccrod.cancer.gov/confluence/display/CCRCRO/Forms+and+Instructions>

8.5.1 Maternal exposure

If a patient becomes pregnant during the course of the study, the study treatment should be discontinued immediately, and the pregnancy reported to the Sponsor no later than 24 hours of when the Investigator becomes aware of it. The Investigator should notify the Sponsor no later than 24 hours of when the outcome of the pregnancy become known.

Pregnancy itself is not regarded as an SAE. However, congenital abnormalities or birth defects and spontaneous miscarriages that meet serious criteria ([8.1.2](#)) should be reported as SAEs.

The outcome of all pregnancies (spontaneous miscarriage, elective termination, ectopic pregnancy, normal birth, or congenital abnormality) should be followed up and documented.

8.5.2 Paternal exposure

Male patients should refrain from fathering a child or donating sperm during the study and for 30 days after the last dose of LB100.

Pregnancy of the patient's partner is not considered to be an AE. However, the outcome of all pregnancies (spontaneous miscarriage, elective termination, ectopic pregnancy, normal birth, or

Abbreviated Title: Phase II Study LB100 gliomas

Version Date: 06/02/2022

congenital abnormality) occurring from the date of the first dose until 30 days after the last dose should, if possible, be followed up and documented.

8.6 REGULATORY REPORTING FOR STUDIES CONDUCTED UNDER CCR SPONSORED IND

Following notification from the investigator, CCR, the IND sponsor, will report any suspected adverse reaction that is both serious and unexpected. CCR will report an AE as a suspected adverse reaction only if there is evidence to suggest a causal relationship between the study product and the adverse event. CCR will notify FDA and all participating investigators (i.e., all investigators to whom the sponsor is providing drug under its INDs or under any investigator's IND) in an IND safety report of potential serious risks from clinical trials or any other source, as soon as possible, in accordance to 21 CFR Part 312.32.

All serious events will be reported to the FDA at least annually in a summary format.

8.7 SPONSOR PROTOCOL DEVIATION REPORTING

A Protocol Deviation is defined as any non-compliance with the clinical trial Protocol, Manual of Operational Procedures (MOP) and other Sponsor approved study related documents, GCP, or protocol-specific procedural requirements on the part of the participant, the Investigator, or the study site staff inclusive of site personnel performing procedures or providing services in support of the clinical trial.

It is the responsibility of the study Staff to document any protocol deviation identified by the Staff or the site Monitor in the CCR Protocol Deviation Tracking System (PDTs) online application. The entries into the PDTs online application should be timely, complete, and maintained per CCR PDTs user requirements.

In addition, any deviation to the protocol should be documented in the participant's source records and reported to the reviewing IRB per their guidelines. OSRO required protocol deviation reporting is consistent with E6(R2) GCP: Integrated Addendum to ICH E6(R1): 4.5 Compliance with Protocol; 5.18.3 (a), and 5.20 Noncompliance; and ICH E3 16.2.2 Protocol deviations.

9 CLINICAL MONITORING

Clinical site monitoring is conducted to ensure:

- that the rights of the participants are protected;
- that the study is implemented per the approved protocol, Good Clinical Practice and standard operating procedures; and
- the quality and integrity of study data and data collection methods are maintained.

Monitoring for this study will be performed by NCI CCR Office of Sponsor and Regulatory Oversight (OSRO) Sponsor and Regulatory Oversight Support (SROS) Services contractor. Clinical site monitoring activities will be based on OSRO standards, FDA Guidance E6(R2) Good Clinical Practice: Integrated Addendum to ICH E6(R1) March 2018, and applicable regulatory requirements.

Details of clinical site monitoring will be documented in a Clinical Monitoring Plan (CMP) developed by OSRO. CMPs will be protocol-specific, risk-based and tailored to address human

subject protections and integrity of the study data. OSRO will determine the intensity and frequency of monitoring based on several factors, including study type, phase, risk, complexity, expected enrollment rate, and any unique attributes of the study and the site. The Sponsor will conduct a periodic review of the CMP to confirm the plan's continued appropriateness. A change to the protocol, significant or pervasive non-compliance with GCP, or the protocol may trigger CMP updates.

OSRO SROS Monitoring visits and related activities will be conducted throughout the life cycle of each protocol. The first activity is before the study starts to conduct a Site Assessment Visit (SAV) (as warranted), followed by a Site Initiation Visit (SIV), Interim Monitoring Visit(s) (IMVs), and a study Close-Out Visit (COV).

Some monitoring activities may be performed remotely, while others will occur at the study site(s). Monitoring visit reports will describe visit activities, observations, and associated action items or follow-up required for resolution of any issues, discrepancies, or deviations. Monitoring reports will be distributed to the study PI, NCI CCR QA, CCR Protocol Support Office, coordinating center (if applicable), and the Sponsor regulatory file.

The site Monitor will inform the study team of any deviations observed during monitoring visits. If unresolved, the Monitor will request that the site Staff enter the deviations in the CCR Protocol Deviation Tracking System (PDTs) for deviation reporting to the Sponsor and as applicable per institutional and IRB guidance.

10 STATISTICAL CONSIDERATIONS

The primary objective of this study is to determine the PK response of LB100 in glioma tissue. The PK response is defined as a binary endpoint indicating the presence/absence of LB100, and will be established by measuring the level of LB100 in resected tumor tissues. This two-stage study is designed to define a significant PK effect with an expected target PK response rate of 40% across patients. The expected 40% response rate is based on preliminary in vitro and animal studies.

Up to 25 patients may be enrolled to obtain 8 evaluable patients. Five patients will be initially treated. If one of five demonstrates a PK response, three additional subjects will be enrolled. PK effect will be declared to be significant if at least 2 of the 8 patients demonstrate a PK response. This yields 87% power to detect a 40% PK response rate across patients, with an overall 10% false positive rate under the null hypothesis that the agent has no biologic effect([17](#)).

The PK parameters, including C_{max} , AUC and elimination half-life time $t_{1/2}$, will be estimated based on standard PK modeling.

PD response is defined as statistically significant elevation of phospho-protein expression in treated tumor tissues compared to untreated glioma specimens. Tissue samples obtained with the initial surgical exposure of the tumor OR material obtained prior to LB100 infusion will be used as control. Untreated inter-patient baseline variance of phospho-protein expression and standard deviation (SD) will be calculated. Post-treatment PD effect (as measured by increase in tumor tissue phospho-protein expression) difference greater than 2.5 times the baseline SD is statistically significant at the .05 significance level. Due to relatively small sample size, t-

Abbreviated Title: Phase II Study LB100 gliomas

Version Date: 06/02/2022

distribution is to be used to calculate the cutoff defining the PD response. The frequency of PD response and its 95% confidence interval will be estimated.

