3 STUDY IMPLEMENTATION

3.1 STUDY DESIGN

This is a two stage Phase II, open label, single institution study to determine the PK and PD profile of LB100 in the setting of gliomas. Patients who are planned for craniotomy will be enrolled if they meet the inclusion criteria. Patients will be admitted to the Clinical Center for the surgery. Tumor tissue will be sampled as part of neurosurgical procedure. LB-100 will be infused over 2 hours (+/- 15 minutes) via IV infusion 2 to 4 hours before surgery. The dose established from a Phase I study will be 2.33 mg/m². Because the tumor resection phase of the craniotomy for

[figure not shown]
Abbreviated Title: Phase II Study LB100 gliomas

Version Date: 06/02/2022

recurrent gliomas typically lasts from one to 5 hours, tumor tissue will be sampled at multiple time points as clinically indicated. The exact time points of tissue removal from LB100 infusion will be recorded by a member of the study team in the OR. Plasma sampling for PK measurements of LB100 will be performed on all participating subjects. (See section **5.1**).

Up to 25 patients may be enrolled to obtain 8 evaluable patients. Five patients will be initially treated. If one of five demonstrates a PK response, 3 additional subjects will be enrolled. PK effect will be declared to be significant if at least 2 of the 8 patients demonstrate a PK response (Presence of LB100 in tumor tissue). Participants whose pathology demonstrates treatment effect or not active tumor will be replaced.

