3.1.1 Design/Schema

3.2 DRUG ADMINISTRATION

LB-100 will be infused over 2 hours (+/- 15 minutes) via IV infusion. The dose established from a Phase I study will be 2.33 mg/m². At the end of infusion, each subject will have an EKG (within 30 minutes of the end of infusion).

Abbreviated Title: Phase II Study LB100 gliomas

Version Date: 06/02/2022

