3.7.2 Off-Study Criteria

- Screen failure
- Pathological evaluation demonstrates treatment effect (e.g. necrosis or inflammation as a result of therapy) rather than tumor recurrence, PK and PD evaluations will not be performed in these subjects. However, given presurgical exposure to LB100 patient will still be followed for AEs as noted in section **6.1**.
- Completed study follow-up period
- Participant requests to be withdrawn from study
- Loss of capacity to provide consent
- Investigator Discretion

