5.1.1.1 Blood

Plasma PK: Plasma sampling for PK measurements of LB100 will be performed on all participating subjects. Blood samples for the determination of plasma levels of LB-100 and its metabolite LB100 M (endothall) will be obtained from each patient via 6mL chilled sodium heparin tube (BD, Franklin Lakes, NJ). At each time point, 6 mL will be drawn into a chilled heparin collection tube and kept on ice. Blood should be processed into plasma within 30 minutes of collection. Once plasma is aliquoted, 5N sodium hydroxide (NaOH) will be added at a ratio of 1:100 relative to plasma (e.g., 0.02 mL of 5N NaOH added to 2 mL plasma); the final NaOH concentration will be 50 mM in plasma. The fortified plasma will then be aliquoted into equal volumes in cryovials and frozen at -70° C until the time of analysis. Plasma PK evaluation will be performed in the [name] Laboratory as described in **5.1.3**

Blood samples will be collected at the following time points: 1*) Pre-dose; 2*) End of infusion (2 hours post-start); 3*) 30 minutes post LB100 infusion completion; 4*) 1 hour post LB-100 infusion completion; 5*) 2 hours post LB100 infusion completion; 6) 4 hours post LB100 infusion completion; 7) 8 hours post LB100 infusion completion; 8) Other blood samplings will take place at the time post-infusion tissues are retrieved. Note: * indicates that the sample may be obtained during the operative procedure. Later time points are after leaving the OR. All blood collection specified within time is allowed for +/- 15 minutes windows, with the exception of the pre-dose sample. The pre-dose blood sample may be collected any time within 48 hours prior to drug administration. Also, blood PK is at physician discretion. The primary purpose of the study is to determine the **tissue** PK (brain tumor).

Bioanalytical measurements will be conducted on an ultra HPLC-MSMS system using an assay developed and validated by the Clinical Pharmacology Program.

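### Section 10 accepts initial-exposure tumour tissue as an untreated PD control although Section 3.1 makes it post-dose; any resulting bias is toward no PD effect, of unknown and possibly zero size

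*Combined protocol and SAP*

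**What the plan says.** Section 10 sets the comparison: "PD response is defined as statistically significant elevation of phospho-protein expression in treated tumor tissues compared to untreated glioma specimens". The cutoff is 2.5 times a baseline SD, for which "Untreated inter-patient baseline variance of phospho-protein expression and standard deviation (SD) will be calculated". The control rule is: "Tissue samples obtained with the initial surgical exposure of the tumor OR material obtained prior to LB100 infusion will be used as control". The conjunction makes initial-exposure tissue an alternative to pre-infusion material, and nothing restricts it to patients not yet dosed.

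On timing, Section 3.1 states: "LB-100 will be infused over 2 hours (+/- 15 minutes) via IV infusion 2 to 4 hours before surgery". Section 3.7.2 agrees ("given presurgical exposure to LB100 patient will still be followed for AEs"), and the study calendar in Section 3.4 lists LB100 in the pre-treatment column.

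Other places fit an infusion during the operation. The same calendar puts the end-of-infusion EKG in the craniotomy column. Section 5.1.1.1 stars the plasma draws from pre-dose to 2 hours after infusion, explaining that the star "indicates that the sample may be obtained during the operative procedure", and adds: "Later time points are after leaving the OR". Section 5.1.2.11 describes PD tissue resected both before and after infusion.

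Section 5.1.2.11 also gives the preclinical time course: a phospho-protein rise at 4 hours at the earliest, reliable by 8 hours, and kept for about 40 hours. It does not say whether those hours run from the start or the end of exposure.

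**The concern.** A specimen taken after dosing began cannot stand for untreated tissue, yet the rule as written lets it do so. If it already carries part of the drug effect, the treated-minus-control difference shrinks. If such specimens also enter the baseline SD alongside naive ones, the cutoff rises. Both act toward fewer PD responses, so target modulation (objective 1.1.2.2) could be under-reported. The PBMC–tumour comparison (objective 1.1.2.5) uses the same tumour measure.

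Section 10 also does not say whether the reference is pooled across patients or taken within each patient. With a pooled reference, a contaminated baseline shifts every patient's result. A null PD finding could then mean either no target modulation or a control that was not naive, and the plan gives no way to tell these apart.

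**Working it through.** **1. The plan's own figures.** Primary PK design (go on with at least 1 of 5, succeed with at least 2 of 8) at a 40% rate: P(at least 2 of 8) = 0.894. Subtract the paths with 0 of 5 and then at least 2 of 3: 0.6^5 × 0.352 = 0.027. The result is 0.866, matching the stated 87%. PD tissue does not enter this calculation.

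PD cutoff: t(0.975, 7 df) × √(1 + 1/8) = 2.508. This reproduces 2.5 SD as one new value against a pooled baseline of eight, two-sided. The plan does not state that model; it is used below because it fits.

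**2. When the control is taken.** Assume 1 hour from start of surgery to tumour exposure and a nominal 2-hour infusion. Section 3.1 does not say whether its 2 to 4 hours run from infusion start or end.

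| Section 3.1 refers to | Hours after infusion start | Hours after infusion end |
|---|---|---|
| start of infusion | 3–5 | 1–3 |
| end of infusion | 5–7 | 3–5 |

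**3. Share of effect already in the control.** Assume a linear rise, f(t) = (t − 4)/4 between 4 and 8 hours. Windows of 1–3 and 3–5 hours give f from 0 to 0.25. Only the 5–7 hour window gives more (0.25 to 0.75), and the point does not rely on it. For controls spread evenly over 3–5 hours, the mean f is (1/2) × (1/8) = 0.0625, about 6%.

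**4. Illustrative effect on PD response.** With a true effect of E baseline SDs and treated tissue at full effect, P = 1 − Φ((2.5 − (1 − f)E)/√(9/8)).

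| E (assumed) | f = 0 | f = 0.25 | f = 0.50 |
|---|---|---|---|
| 3 | 68% | 41% | 17% |
| 4 | 92% | 68% | 32% |
| 5 | 99% | 88% | 50% |

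At E = 4 and f = 0.0625, P = 1 − Φ((2.5 − 3.75)/1.061) = 88%. The loss is therefore 4 points at the mean carry-over and 24 points at the 5-hour edge. With one independent control per patient instead (variance 2), the E = 4 row becomes 86%, 64% and 36%.

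**5. Mixed baseline.** Suppose 4 of 8 baseline specimens are post-dose and E = 4. The baseline mean shifts by 2f and the variance is 1 + (8/7)(0.25)(4f)². At f = 0.25 the SD is 1.13, the cutoff 2.83 and P = 73%. At f = 0.50 they are 1.46, 3.66 and 27%.

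**6. A limit of the illustration.** On the same ramp, treated tissue reaches full effect only at 8 hours. With a fully naive control and E = 4, treated tissue at 6 hours gives 1 − Φ((2.5 − 2)/1.061) = 32%, and at 5 hours 8%. The 92% is therefore not a general benchmark.

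**The case against.** The strongest reply is that the size is almost wholly assumed. Effect size, opening time, linear rise, pooled baseline of eight and full-effect treated tissue are not in the documents, and the onset data are preclinical. One of the windows relied on (1–3 hours) gives no loss at all, and the 24-point figure arises only at the edge of the others. Step 6 shows that early treated sampling could by itself depress the PD frequency more than the control does. All of this stands, so the percentages cannot rank severity.

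Second, the timing conflict can be read down. If the infusion starts 2 hours before surgery, the end-of-infusion to 2-hour draws can fall in the operating room without contradicting Section 3.1, and the calendar's craniotomy column may simply mean the day of surgery. This stands in part. The star on the pre-dose draw and the wording about tissue resected before infusion still fit poorly, and no section says which schedule defines the control.

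Third, SD inflation requires post-dose tissue to be counted as untreated, against the plain word. That is fair, but the control rule invites it.

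Fourth, the endpoint is secondary, no go/no-go rule rests on it, and with eight patients the exact intervals are wide (7/8: 47–100%; 5/8: 24–91%). The bias would not create a false PD claim. This limits the consequence but does not settle which specimens are untreated.

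Fifth, early same-surgery tissue is matched and handled identically, whereas archival or external tissue brings preservation differences of unknown direction. This stands and shapes the fix.

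**Conclusion.** The point holds as a definitional defect: following Section 10 on the Section 3.1 schedule can label a treated specimen as untreated. Where that happens, drug effect carried in the control biases the secondary PD-response frequency toward null. This direction assumes the effect does not fall between the control and later specimens, which the roughly 40-hour maintenance supports; non-drug changes during surgery could act either way. The size is unknown and may be zero or small, and every percentage above is an illustration.

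A reader might infer that every control is contaminated, that about a quarter of PD responses will be lost, or that one of the infusion schedules is wrong. The documents support none of these. Pre-infusion material is also allowed, initial-exposure tissue could be naive if the infusion runs during surgery, and onset at 4 hours at the earliest permits no carry-over. No view is taken on which schedule is right. The primary PK endpoint, the two-stage rule and the 87% power are untouched. The change should be made, but the point is not critical.

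**What to change.** Reconcile Sections 3.1, 3.4, 5.1.1.1, 5.1.2.11 and 10 on when infusion and tissue removal occur relative to each other. Then amend Section 10:

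- Count as untreated control, and use for the baseline SD and the t-based cutoff, only tissue collected before any LB100 exposure and preserved and assayed comparably to the treated specimens.
- Classify initial-exposure tissue by its recorded time from infusion. If taken before the infusion starts, it qualifies as untreated. If taken after, keep it as the earliest timed post-dose sample and report contrasts against it separately as within-surgery change, not as PD response.
- State whether the reference is pooled or within-patient, and match the denominator of the frequency and its 95% CI: all treated evaluable patients if pooled, those with a naive control if within-patient.
- Report the time from infusion for every PD specimen.

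The wording change is cheap, because Sections 3.1 and 5.1.1.2 already require these times to be recorded. The cost is information: fewer naive controls, hence a less precise SD if pooled or a wider CI if within-patient. Archival material may not fill the gap. PD tissue is flash frozen (Section 5.1.1.2), while the pathology archive is paraffin with excess tissue discarded after up to three months (Section 5.2.1.1), and for earlier operations elsewhere the plan requests slides (Section 2.2.1). Such specimens should not replace matched same-surgery tissue without checking for preservation differences, which is why both contrasts should be reported.
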